Blackpool CCG and Fylde & Wyre CCG rolled out ECS and EPC together as two complementary MDT models for patients in the highest and second highest risk groups, respectively, with some clinical judgement applied to final referrals after initial stratification using the CPM.¹⁶ The NEHF vanguard covers the same area as the CCG, and the ICTs targeted the patients who were considered by referring professionals to have the highest need, to be at greatest risk of going into crisis and who would most benefit from multidisciplinary support, although there was some local variation in targeting between the five locality teams. In both Fylde Coast and NEHF, referrals typically came from GPs. In Fylde Coast, final enrolment decisions were determined by a clinical assessment carried out by the MDT and patient consent to starting the service. In NEHF, consent was obtained before referral, and therefore all patients in NEHF referred to an ICT are considered enrolled in the programme.

Original study designs

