| Target population Procedure for determining eligibility Risk stratification | Originally aimed at the cohort with highest risk for hospital use: - 60+ years old - at least 2 long-term conditions (LTCs) from a pre-specified list [*] - predicted CPM [†] risk score ≥20 . Eligibility criteria amended in Feb 2016 to allow individuals at least 2 prior A&E admissions or 2 out-of-hospital contacts within last 2 months, instead of risk score ≥20. | Originally aimed at a moderate or 'second highest' risk cohort, alongside ECS, with patients: - 16+ years old - predicted CPM [†] risk score ≥20 - attention to mental ill health and/or difficult personal or social circumstances. Expanded to include professional clinical judgement about anyone who could benefit from increased support. | Intended to reach patients with highest need and at highest risk of going into crisis, primarily assessed by professional clinical judgement. In practice, health professionals also selected patients based on who they considered would benefit most from a multidisciplinary approach. Risk scores (using Johns Hopkins ACG system) initially planned but ultimately not used during the period of the study, except for a small minority of cases. Farnham used risk stratification and other patient data from March 2017. |
| Median age (IQR) of MDT patient | 80 years (73, 85) | 76 years (63, 85) | 81 years (72, 87) |
| Source of referrals | Originally only GPs. Later broadened to hospital and community professionals. | Most referrals were made by GPs, but also possible from others (community, mental health and social care staff). Blackpool patients could self-refer but this was rare. | Most referrals were made by GPs, but also possible from others (community, mental health and social care staff). |
| Assessment of eligibility | MDT assessed eligibility; patient or service could refuse enrolment for various reasons. ECS patients could not simultaneously be on EPC. Typically, where a single individual did receive care from both MDTs, EPC was used as a step-down service from ECS. | | Health professionals referring used their clinical assessment. Patients could refuse referral; all referred patients were seen by MDT. |

^{*} Across coronary arterial disease (CAD), atrial fibrillation, congestive heart failure (CHF), chronic obstructive pulmonary disease (COPD), diabetes, dementia.

t Combined Predictive Model using inpatient, outpatient, A&E and GP data.

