| Health variables* Elixhauser list of comorbidities, identified in the pre-period Specific comorbidities linked to frailty, identified in the pre-period Selected comorbidities predictive of hospital emergency admission, as identified by the IPAEOPGP model, identified from SUS data in the pre-period: Charlson index, myocardial infarction, cerebrovascular disease, dementia and cognitive dysfunction Number of Elixhauser comorbidities in the pre-period Number of frailty comorbidities in the pre-period Mental ill health and severe mental ill health (as defined in NEHF SAP) | Number of Elixhauser comorbidities in the pre-period did not count peripheral vascular disease in error Different definition of mental ill health in Fylde Removed: - Frailty variables delirium, senility and dementia were redundantly included when these were also captured using the composite variable cognitive impairment - Number of comorbidities (frailty, Elixhauser and variables from IPOPAEGP) due to double counting - The risk stratification score and the associated derived GP data for the risk scores (frailty score and list of long-term conditions) - Some overlapping variables, eg for mental ill health and rheumatoid arthritis | History of peripheral vascular disease (an Elixhauser comorbidity) was previously omitted in error Number of Elixhauser comorbidities in the pre-period did not count peripheral vascular disease in error For Elixhauser comorbidities where conditions were differentiated by level of complexity, a patient could be recorded as having both levels. For the total number of Elixhauser comorbidities, patients recorded as having both cancer with and without metastases were double counted (in both NEHF and Fylde) |
| SupportLiving in a care home | Not included in original study | Included in the original study but using an older address matching algorithm |
| Time periodIndex date/period (by quarter) | Unchanged | |
| 'Counterfactual' level of care available outside the MDT CCG Neighbourhood/locality in which the patient is registered with a GP | Unchanged | |

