| Social context Living alone Living with somebody with dementia or frailty[†] Recently living alone (change in last X months)[†] Bereavement in last X months[†] Number of moves in last 12 months | New variables to be refined and added as a key output of the pooled analysis – ATT estimated effects from the previous evaluations may or may not be robust to inclusion of such social context factors when identifying and matching/weighting for potential controls. If ATTs are not robust, the analysis will demonstrate clear evidence of previously unobserved confounding | |

Note: these are potential covariates and may not all have been included in both the matching and regression stages in the original studies (see technical reports for further details).

* Health variables are identified from hospital records in the 3-year pre-period.

t Exploratory analysis will establish exact definition (see section on social context).

The Elixhauser and Charlson lists of comorbidities are routinely used for risk adjustment.^{57,58,60,66} The Elixhauser list is broader than the Charlson list and consists of the following 30 comorbidities: congestive heart failure; chronic pulmonary disease; hemiplegia or paraplegia; metastatic solid tumour or metastatic cancer; acquired immune deficiency syndrome or human immunodeficiency virus; peripheral vascular disease; cardiac arrhythmias; valvular disease; pulmonary circulation disorders; hypertension (uncomplicated); hypertension (complicated); other neurological disorders; diabetes (uncomplicated); diabetes (complicated); hypothyroidism; renal failure; liver disease; peptic ulcer disease (excluding bleeding); lymphoma; solid tumour without metastasis, rheumatoid arthritis or collagen vascular diseases; coagulopathy; obesity; weight loss; fluid and electrolyte disorders; blood loss anaemia; deficiency anaemia; alcohol abuse; drug abuse; psychoses; depression.^{57,58} Most of the comorbidities on the Charlson list are covered by the Elixhauser list.^{58,60,66} One notable exception is dementia; therefore, dementia is included separately (see Table 5).

The following list of comorbidities is considered linked to frailty: anxiety or depression; functional dependence; falls and significant fracture; incontinence; mobility problems; pressure ulcers; and cognitive impairment (composite of delirium, dementia and senility), consistent with other IAU analyses.^{59,67}

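### Coronary artery disease counted towards ECS entry, but Table 5 captures it only in part (myocardial infarction and the Charlson index), so coronary disease without a recorded infarction is not directly balanced

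*SAP*

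**What the plan says.** - **Entry rule.** SAP Table 1 (Target population, ECS) asks for age 60 or over, "at least 2 long-term conditions (LTCs) from a pre-specified list" and a risk score of at least 20. The footnote names the list: "Across coronary arterial disease (CAD), atrial fibrillation, congestive heart failure (CHF), chronic obstructive pulmonary disease (COPD), diabetes, dementia".
- **Amendment.** From February 2016 patients could qualify through prior A&E admissions or "2 out-of-hospital contacts within last 2 months, instead of risk score ≥20". As printed, this replaces the risk-score limb only, so the two-condition limb stays.
- **Judgement.** The Background section adds that ECS and EPC were rolled out "with some clinical judgement applied to final referrals after initial stratification using the CPM". Entry was not purely algorithmic.
- **Covariates.** Table 5 (Health variables) offers the Elixhauser conditions, the frailty conditions, counts of each, mental ill health, and a short extra list: "Charlson index, myocardial infarction, cerebrovascular disease, dementia and cognitive dysfunction". All come from hospital records over three years. For Fylde, the risk score and its GP-derived frailty score and list of long-term conditions are removed.
- **Elixhauser list.** The notes to Table 5 say "The Elixhauser list is broader than the Charlson list and consists of the following 30 comorbidities" and print them.
- **Control pools.** The Study cohorts and Exploratory analyses sections keep the inclusion criteria and control pools of the original studies, except that age slimming is harmonised.

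**The concern.** A condition that helped decide who entered ECS, and that plausibly raises emergency admissions, should be among the balanced covariates if hospital records can supply it. CAD is the only one of the six without its own flag or a flag that contains it. If treated ECS patients carry more non-infarction CAD than their weighted controls, the comparison makes ECS look worse than it is. That is the direction of the unexplained increase that hypothesis H1 (residual confounding) sets out to probe. ECS supplies 1,626 of the 5,411 treated patients.

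The planned checks would not isolate the gap. Standardised-difference plots cover the covariates supplied to the algorithm, and the SAP itself notes that entropy balancing drives those differences to about zero by construction. The risk-score check varies the risk score, and its remedy is to impute scores for NEHF. Neither step adds CAD.

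**Working it through.** **Step 1. Reproduce the list size.** Splitting the printed Elixhauser list at its semicolons gives 30 items, as stated (31 if the entry joining solid tumour and rheumatoid arthritis is split at its comma). None mentions coronary disease, ischaemia, angina or infarction. The frailty list has no coronary entry either.

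**Step 2. Map the six conditions to Table 5.**

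| ECS condition | Table 5 cover |
|---|---|
| Congestive heart failure | Own flag |
| COPD | Chronic pulmonary disease (broader) |
| Atrial fibrillation | Cardiac arrhythmias (broader): "peripheral vascular disease; cardiac arrhythmias; valvular disease" |
| Diabetes | Two flags |
| Dementia | Own flag |
| CAD | Myocardial infarction only (narrower), plus a share in the Charlson index |

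Five of six have a containing flag. CAD has a narrower one, and a summary index does not isolate a single condition.

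**Step 3. Does the missing flag leave a gap?** The SAP gives no prevalences, so every input here is an assumption: pool CAD prevalence 8%, 15% or 25%; the other five conditions 3% to 20%; infarction recorded in 20%, 40% or 60% of CAD; latent correlation between conditions 0 or 0.3. Treated patients are drawn from people with at least two of the six, and controls are entropy-balanced on means. Ranges over the 18 scenarios:

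| Balanced on | CAD, treated | CAD, weighted controls | Control weight with fewer than two of six |
|---|---|---|---|
| Five flags, no coronary item | 44–68% | 8–42% | 37–44% |
| Five flags + infarction (as Table 5) | 44–68% | 15–53% | 33–41% |
| Five flags + CAD | 44–68% | 44–68% | 27–36% |

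The infarction flag helps but does not close the gap. Scenario by scenario, the shortfall with infarction balanced runs from 12 points (55% − 43%) to 29 points (60% − 31%).

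**Step 4. From a prevalence gap to a bias.** If CAD multiplies the admission rate by RR, and its prevalence is p1 in treated patients and p0 in weighted controls:

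bias factor = (1 + (RR − 1)·p1) / (1 + (RR − 1)·p0)

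Take a middle scenario (p1 = 0.55, p0 = 0.38). RR = 1.3 gives 1.165/1.114 = 1.046, and RR = 1.5 gives 1.275/1.190 = 1.071. These ignore the prior-admission covariates in Table 5.

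**Step 5. Add prior admissions.** Two illustrations balance them as well. Both assume pool prevalences of 10–30% per condition and selection that rises with prior admissions.

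- *CAD keeps an independent effect.* Infarction in 30–50% of CAD; RR of 1.3–1.5 assumed to apply in full to the remaining gap. The gap is 6–19 points in 12 scenarios, and the bias factor about 1.02–1.09.
- *CAD acts alike on past and future admissions.* Infarction in 30% of CAD; RR 1.3–1.5; gamma person-level heterogeneity (shape 1); base rate 0.4–0.8. The gap is still 7–20 points, but adding a CAD flag moves the ECS rate ratio by only about 0.1–2.8%, because balancing past admissions already removes most of the effect.

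The illustrations agree on direction. They differ on size because they differ on how much of CAD's effect is already visible in past admissions.

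**Step 6. Weight in the pooled result.** ECS is 1,626/5,411 = 30% of treated patients. Weighting by patient numbers, even a 9% bias in ECS becomes about 0.30 × 9% = 2.7% overall.

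**The case against.** The strongest reply is that this is a refinement, not an error. Table 5 lists potential covariates, infarction and the Charlson index already give partial cover, and atrial fibrillation and COPD are also represented only by proxy. Prior emergency admissions, A&E attendances and length of stay are in the table and would absorb much of what CAD does to the outcome. The risk-score check might pick up some of the loss if the GP-derived list held CAD. Clinical judgement and GP-only diagnoses further loosen the link between hospital-coded conditions and entry.

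Most of this stands, and it limits the size of the point. It does not remove the point. The SAP adds dementia separately because the Elixhauser list lacks it, and adds other hospital-identifiable predictors for the same reason; CAD is the same kind of gap and was an entry condition as well. It comes from the same hospital records in all three areas, so comparability with NEHF gives no ground for leaving it out.

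A reader might also infer that weighted controls fail the two-condition rule because CAD is missing. The documents do not support that. Balancing means does not enforce a joint rule: with CAD added, 27–36% of control weight still fell below two conditions in Step 3. The criteria that defined the ECS control pool sit in the original study protocols, which are not shown, so some restriction by condition may already apply. Nor is failing the rule a bias in itself: the effect on the treated needs balance on outcome predictors, not controls who meet the entry criteria.

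**Conclusion.** The point holds as a gap in covariate coverage. CAD without a recorded infarction is a measurable ECS selection variable that Table 5 does not directly balance. It is likely to be under-represented among weighted ECS controls, and if CAD raises emergency admissions, the ECS effect is biased upwards.

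The size cannot be fixed from the SAP. The illustrations with prior admissions balanced span roughly 0% to 9% on the ECS rate ratio. They rest on assumed prevalences, correlations, infarction shares and CAD rate ratios, and they are not bounds. It would be tempting to turn such a range into a corrected version of the reported 27% increase in ECS emergency admissions. The documents do not support any such figure, and nothing here shows that confounding by CAD explains that increase. The change is worth making because it is cheap and bears directly on H1.

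**What to change.** 1. Add to Table 5, for all three studies, a coronary or ischaemic heart disease flag from any hospital diagnosis in the 3-year pre-period.
2. For the ECS contrasts, also balance the hospital-coded count of the six qualifying conditions in categories (0, 1, 2, 3+), where the algorithm converges. The flag alone does not align the count; the categories do so by construction.
3. Report the share with two or more of the six among treated ECS patients and among weighted controls. This also shows how far hospital coding reproduces the entry rule, given GP-only diagnoses and clinical judgement.

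**Cost.** SAP wording, plus one flag and one four-level count from diagnoses already extracted. That is about four more balancing constraints (one for the flag, three for the count) for 1,626 treated patients, with slightly more variable weights. If the count makes the weights extreme, keep the flag and report the shares without balancing the count.

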| Emergency admissions [*] | 27% higher (15% to 41% higher) | 42% higher (29% to 56% higher) | 43% higher (23% to 67% higher) |
| Chronic ACS emergency admissions [*] | 62% higher (33% to 98% higher) | 32% higher (4% to 66% higher) | 105% higher (32% to 222% higher) |
| UCS emergency admissions* | 24% higher (3% to 48% higher) | 46% higher (21% to 75% higher) | 76% higher (35% to 129% higher) |
| Average length of emergency stay, nights [*] | N/A | N/A | 33% higher (8% to 63% higher) |
| Emergency hospital bed days | 8% higher (9% lower to 28% higher) | 57% higher (31% to 88% higher) | N/A |
| Emergency readmissions within 30 days of discharge | N/A | N/A | 4% higher (11% lower to 21% higher) |
| Elective admissions (ordinary or non-regular day admissions) | 8% higher (5% lower to 24% higher) | 2% lower (14% lower to 10% higher) | 24% lower (2% to 41% lower) |
| Elective bed days | 1% higher (34% lower to 54% higher) | 18% lower (25% to 10% lower) | N/A |
| Outpatient attendances | 10% higher (4% to 17% higher) | 11% higher (5% to 16% higher) | 3% higher (8% lower to 17% higher) |
| Deaths in hospital | 43% higher (2% to 100% higher) | 21% higher (12% lower to 67% higher) | 27% lower (42% lower to 2% higher) |
| Deaths [*] (placebo test) | 4% higher (16% lower to 28% higher) | 58% higher (33% to 89% higher) | 22% higher (12% lower to 68% higher) |

Note: all relative differences are rate ratios, apart from deaths and deaths in hospital, which are odds ratios.

Outcomes proposed for the pooled analysis.

*

18

Potential causes of increased emergency hospital use for patients enrolled in MDTs

There are several plausible hypotheses consistent with the results we observed and previous research^{1,10}:

- H1 Residual unobserved confounding (differences in eg social context, end of life)
- H2 Patient-specific effects (subgroup heterogeneity)
- H3 Limited 'impactability' of riskiest patients
- H4 Delayed impact caused by patient and/or provider factors
- H5 Induced demand from clinical risk aversion
- H6 Hospital use does not adequately measure quality.

H1. Residual unobserved confounding accounts for impacts, as MDT patients were still different from their matched controls in unseen but important ways

Unseen differences between the respective intervention and matched control groups could potentially account for some or even all the difference in hospital use between the intervention and control groups (unobserved confounding). This is the case when the matched control patients appear very similar to the intervention patients but have important unseen differences that may impact on their eligibility for MDTs as well as their hospital use. The risk of unobserved confounding is always a limitation of observational studies but is a particular concern where the intervention was available for the control individuals but they were not selected, even though they had similar observable characteristics. This is the case in these studies: controls were from the same areas as the patients enrolled in MDTs and appear very similar, but were not referred to an MDT (in the case of NEHF) or not referred for assessment and potential enrolment in an MDT (in the case of ECS and EPC).

For the original evaluations, although we adjusted for factors such as age, level of deprivation, LTCs and prior hospital use, we may not have captured other important factors that contributed to the decision to refer to an MDT. We found that there was strong statistical evidence that patients enrolled on EPC had a higher rate of death during the follow-up period, as compared to the matched control group. That suggests that there was greater baseline medical risk in this group prior to receiving EPC that could not be accounted for in the accessible data. However, the observed crude risk difference in deaths (3.6 percentage points higher, for an overall crude mortality rate of 10.6%) is highly unlikely to account for the observed differences in hospital activity (approximately 40% greater A&E attendances and emergency admissions among all EPC users as compared to matched controls). EPC patients who died during the follow-up period did not have hospitalisation rates that were over 10 times higher (40% divided by 3.6%) than the matched control group. We can investigate whether nearing end of life may be an unobserved confounder in the original analyses by subsetting patients depending on if they died within 90 days of being enrolled in an MDT/entering the study.

Unobserved confounding was a particular concern in the NEHF study, where health professionals referred patients based predominately on clinical judgement (rather than on objective criteria) on which patients would most benefit from support from a multidisciplinary team, because they were at highest risk and need. This may have been based on information not available in our original data, such as not managing a long-term condition well or being socially isolated, where such factors also included an element of clinical judgement. In Fylde Coast, risk scores were used for selection to both types of MDTs but particularly EPC was aimed at individuals who a GP felt could benefit from increased support because of a lack of family support or other factors that meant they could not effectively manage their own health.

Stokes et al found that when identifying patients for MDTs, medical practitioners felt that the patients' needs were often primarily related to social factors such as isolation, poor housing or living arrangements, and other socio-economic issues.²

One such factor could be social isolation, which has been found to be associated with both increased morbidity and mortality.^{28,29} Social isolation is a concept related to but distinct from loneliness; while loneliness is a subjective feeling associated with actual or perceived isolation, social isolation reflects a lack of social ties, social integration or sense of community.^{28,30}

It is not possible to quantify social isolation in our data, but there is potential to identify proxies of it relating to social context. One of these is whether someone is living alone, and this has been found to be associated with a 50% higher likelihood of visiting A&E than those living with others.¹² However, while living alone could result in social isolation, it is not necessarily the case; approximately one-third of people aged 65 or over live on their own³¹, many of whom may have friends or family living nearby. Therefore, identifying whether somebody is living alone may not be sufficient to identify somebody who is socially isolated. Other, related, factors that may affect health outcomes and a health professional's decision to refer a patient to an MDT may be life events such as a recent bereavement³² or losing one's job. Another factor could be housing instability. Social isolation is also likely to be associated with having LTCs (something we already account for in our analyses) or living and caring for somebody in the family with LTCs, as this can lead to the person being more housebound or having less time available for social interactions or leisure activities, especially if it may not be safe to leave the household member on their own. This may particularly be the case if the person has dementia, serious mental ill health or profound mobility problems. It may also be more difficult to look after one's own health while also caring for somebody else; therefore, this may be important social context to account for in its own right.

If in fact these social context factors were poorly matched in our previous studies, the original evaluations would be limited by biased information and the 'true' impact of these interventions ought to be reassessed in light of the newly observed data. However, it is also plausible that the conclusions from our original evaluations remain unchanged despite including further potential sources of unobserved confounding. Statistically, this issue cannot be eliminated or precisely quantified in an observational study.^{*} Yet careful study designs to evaluate impact can and do replicate the treatment effects of clinical and other health interventions seen from randomised controlled trials^{33,34} and can match real-world experience more closely than the very controlled and sometimes artificial conditions of most trials.³⁶

There are some statistical methods available, eg Rosenbaum bounds (https://cran.r-project.org/web/packages/rbounds/ rbounds.pdf) which calculates how sensitive results are to unobserved confounding. However, these are not currently available for count outcomes.

^{*}

There are several further hypotheses which relate to patients' 'impactability', ie the notion that some people may be more amenable to preventive care and that individuals at the highest overall risk for emergency hospital use do not necessarily correspond with the group of people for whom such hospitalisation can actually be prevented or avoided.³⁶This is related to but distinct from the identification of unmet need and a non-linear impact on hospital use over time, as discussed in the fourth and fifth hypotheses below.

H2. MDTs may be best suited to support specific patient subgroups

MDTs may be better suited to support certain patient subgroups, eg those with serious mental illness, diabetes or heart failure, rather than the general population of individuals who are identified as having high risk of hospitalisation in the following 12 months. It may be more difficult to detect a positive impact overall in evaluations of MDTs serving a broader general population if there is heterogeneity in characteristics and in the MDTs' effect on outcomes.

Although MDTs have been demonstrated to reduce emergency hospitalisation in several randomised trials, this data has been sparse and research protocols were of varying quality and high heterogeneity, eg evidence from the US where system incentives and clinical risk thresholds are quite different from the UK, and studies pre-dating the landmark 2012 Health and Social Care Act in the UK. In both cases, MDTs may be less effective or even counterproductive in England today, due to unignorable differences in how NHS and social care are now organised.

Recent evidence is equivocal about the impact of MDTs on hospital activity. Integrated care interventions in primary and community care settings, including MDTs, have a mixed record of success when applied to patients with general multimorbidity³⁷, including no change in hospital use for 'primary intensive care' case management models in the US.³⁸ Multidimensional assessment and management of older people in primary care does not appear to impact patient outcomes in the UK.³⁹ However, other research, for example a multicentre randomised trial in the north of England, has found greater independence for older people needing rehabilitation when providing community-based MDTs.⁴⁰

Historically, some but not all measures of reduced hospital use – for example shorter length of stay but not lower emergency admissions – have been demonstrated across systematic reviews of international trials in congestive heart failure^{41,42} and stroke⁴³ and with relatively modest impacts in specific UK trials for severe mental illness.^{44,45} Conversely, integrated care managers in the US have previously believed that serious mental ill health makes it less likely that case or disease management will reduce hospital use among patients who have these conditions.³⁶ Integrated care may reduce length of stay and long-term dependency among stroke patients.⁴³

However, even if there are certain conditions that are more amenable to multidisciplinary support, these conditions may not be equally well supported by an MDT that cares for a broader range of conditions and needs as by one specifically targeting patients with a specific diagnosis, particularly if condition-specific staffing and skills are required for intervention effectiveness.

H3. There may be limited scope to reduce or impact emergency hospital use for the highest risk patients, especially those nearing end of life

Linked to the concept of 'impactability', it may be that there is limited scope to reduce emergency hospital use for those identified as being at the highest risk, especially if they are nearing their end of life.^{10,36,46} In qualitative feedback, Fylde Coast MDT staff noted for instance that some patients had elevated 'acuity' and therefore may not have represented a group for whom future hospital use could actually be avoided.¹⁶

If the aim is to reduce emergency admissions, it may be that MDTs should not target the patients identified as at highest risk. There may instead be more scope, especially at a population level, to reduce unplanned hospital use in a lower or more moderate risk group of patients whose long-term conditions have not yet progressed to the most serious or unmanageable stages. MDTs may be able to delay and compress future periods of frailty for a high-impact group of patients, but these may not be the same population that the vanguards were able to identify and target in their initial phase.

The currently available tools for risk stratification are somewhat useful but not definitive for targeting MDTs. While they use extensive data to predict hospital admission, there is still substantial likelihood of false negatives and positives in their use, and most of them do not address impactability directly.^{10,47,48} These tools also cannot capture or report information that is not routinely collected in aggregated NHS data systems but which might be important for targeting MDTs, for instance on social isolation, homelessness, or similar personal circumstances. In some cases, continuous development and improvement of these tools is no longer supported (eg NHS support for continuous development on CPM was halted in 2011), which limits their continued applicability and validity. Such tools may be most useful when deployed alongside clinical judgement to target population health interventions.⁴⁹

H4. MDTs increase hospitalisation initially but can sustain reduced use over a longer time period

Greater hospital use by MDT patients may reflect a real impact that occurs in the year immediately following the intervention, but this may be offset by reduced hospital use over the longer run. In other words, it is possible that the short-run increases we observed are a typical impact of MDTs, but overall these are offset by reductions when considering a longer time period following MDT enrolment.

Such a pattern could be due to MDTs identifying urgent unmet medical needs that might otherwise have only been identified later at a more problematic stage or gone untreated otherwise. It is possible that for many of the people targeted by these MDTs – including those living alone or with other social factors that we have not previously been able to account for – additional care is needed in the short term to stabilise their condition and promote self-management after acute crises (where such crises signal eligibility for potential MDT benefit in the first place), but these interventions show preventive benefits only later over a longer follow-up period of years rather than months. In other words, it may be that reduced hospital use is only observable beyond the median 7–13 months of follow-up in the original IAU evaluations.

Alternatively – or additionally – a change in MDT impact over time may result from programme implementation lag. Consistent with change management theory⁵⁰ complex integrated care programmes like the MDTs may require significantly more time to 'bed in' than allowed for under vanguard funding arrangements. Operational setup and management of complex interventions needs time to take effect, as teams introducing these changes must set up new routines of work, typically within complex institutional bureaucracies, with staff learning from experience and monitoring over time about how to optimise their delivery to achieve strategic aims. For example, in Fylde Coast ECS, the first recruited patients were typically enrolled for longer than current patients, roughly 12 as opposed to 6 months, according to local programme managers¹⁶ and consistent with observed data.⁵ It is thus possible that vanguard MDTs can reduce (and potentially sustain lower) hospital activity over a longer follow-up because the programme can only make these impacts after an initial period of operational start-up and improvement. Alternatively, it may be the case that such a lag is inherent to the effect of MDTs, as provider teams may require a certain number of visits or time with each individual patient in order to optimise the support interventions required to prevent future hospitalisation.

The IAU has previously evaluated the Mid-Nottinghamshire integrated care vanguard, which included, among others, an MDT like the Fylde and NEHF teams.^{*} Evidence from Mid-Nottinghamshire suggests that there was an initial area-level increase in emergency hospital use, which was followed by a decrease in the longer term, apparent only after about 2 years after approval of the vanguard and 4–5 years after initiation of the integrated care transformation programme.⁵¹ This is consistent with at least 2–3 years before a modest reduction or prevention of comparative rates of hospitalisation, as found in other recent peer reviewed research on all the English new care models vanguards¹⁹ and pioneers⁵². In an accompanying study, we plan to replicate the Mid-Nottinghamshire evaluation methods for Fylde Coast CCGs (Blackpool and Fylde & Wyre) and NEHF. If this trend over time holds across the three areas, this would be compelling evidence that integrated care models overall – and potentially also MDTs – take a longer time to generate positive impacts. Further qualitative and process evaluation would be required to quantify the reasons for this delayed impact, but there are at least two plausible explanations.

H5. MDTs may have led to induced demand, from health awareness among patients or heightened risk aversion among professionals

MDTs may have led to patients being more aware of their health needs or risks, or health and care professionals being more risk averse, which in turn led to greater hospital and other service utilisation. This usage may address previously unmet medical need as described above and may therefore be justified or appropriate. However, quality of life impacts – as opposed to service utilisation and mortality trends – can only be measured reliably by further data collection with service users. This phenomenon, whether caused by increased care-seeking by patients or more frequent referral and admission by medical staff, is known as 'supplier induced demand' in health economics. We do not have directly observed or consistent data

*

In Mid-Nottinghamshire, the MDT and other vanguard initiatives were evaluated at an area or whole-population level using synthetic controls rather than as an individually matched study, as no individual-level MDT enrolment data were available. Therefore, a matched-control study was not possible there and it cannot be included in the pooled analysis.

on the clinical risk thresholds or self-reported health awareness across the MDT and matched control sample. As a result, we will not test this hypothesis in the quantitative analyses, but the review of reviews may identify relevant findings in other empirical studies.

H6. Multidisciplinary integrated care teams may improve quality in ways that are not adequately measured by emergency hospital use

The value of integrated care teams may primarily lie in improving other outcomes, such as coordination of care, patients' wellbeing or experience of care or better management of LTCs, rather than reducing emergency hospital admissions. However, these evaluations did not examine, for example, the impact of the MDTs in improving patient-recorded outcome measures of quality of life as they are not routinely collected or recorded in NHS administrative systems.

Unplanned hospital use is an imperfect proxy for quality of care. In many cases, particularly at the end of life, hospital use may not be preventable and may be medically appropriate, eg to check that a chemotherapy has not caused dangerous side effects. In such cases, hospitalisation is essentially inevitable and would not represent a bad outcome for patients, but may represent essential care that improves quality of life by alleviating pain and other symptoms. As such, increases in unplanned (ie unscheduled) hospital use as measured by A&E attendances and emergency admissions could be an appropriate outcome signalling greater quality of care where MDTs address otherwise unmet medical need, and where further complications or worsening of LTCs is not truly preventable. Separate quality improvement literature on end-of-life care has noted the costliness of hospitalisation that motivates many interventions. However, optimal clinical management is nuanced and typically considered in terms of compressing the acute use of medical resources at end of life, ie in reducing length of stay, rather than preventing hospital attendance or admission in the first place for patients with terminal LTCs.⁵³

Objectives of the evaluation

This analysis aims to understand why patients enrolled in MDTs have in general higher emergency hospital use than their comparison groups. As such, we will explore a number of questions relating to the hypotheses above.

